3.3 Prohibitions and Restrictions

Potential subjects must be willing and able to adhere to the following prohibitions and restrictions during the course of the study to be eligible for participation. For restrictions related to concomitant medications, please refer to Section 8.2.

3.3.1 Blood type and Indirect Antiglobulin Test (IAT) results

CD38 is expressed at very low levels on erythrocytes. Preliminary data indicate that daratumumab interferes with IAT (also known as indirect Coombs test) testing and will make complete blood typing difficult while subjects are receiving treatment. In case of an urgent need for a blood transfusion, a blood sample should be obtained before the first infusion of daratumumab and the subject's blood type (ABO, Rh, and IAT) determined. Subjects should be provided a blood type card, which they will carry with them throughout the treatment period.

If the participating site's institution does not have a participant blood type card that they provide, please refer to Appendix G for a template to be printed and completed by the study staff, and given to the participant. Documentation of this process should be included in the source document.

3.4 Inclusion of Women and Minorities

- 3.4.1 Both men and women of all races and ethnic groups are eligible for this trial.

4. REGISTRATION PROCEDURES

4.1 General Guidelines for DF/HCC and DF/PCC Institutions

Institutions will register eligible participants in the Clinical Trials Management System (CTMS)

CONFIDENTIAL

This document is confidential. Do not disclose or use except as authorized.

OnCore. Registrations must occur prior to the initiation of protocol therapy. Any participant not registered to the protocol before protocol therapy begins will be considered ineligible and registration will be denied.

An investigator will confirm eligibility criteria and a member of the study team will complete the protocol-specific eligibility checklist.

Following registration, participants may begin protocol therapy. Issues that would cause treatment delays should be discussed with the Overall Principal Investigator (PI). If a participant does not receive protocol therapy following registration, the participant's registration on the study must be canceled. Registration cancellations must be made in OnCore as soon as possible.

4.2 Registration Process for DF/HCC and DF/PCC Institutions

DF/HCC Standard Operating Procedure for Human Subject Research Titled *Subject Protocol Registration* (SOP #: REGIST-101) must be followed.

4.3 General Guidelines for Other Investigative Sites

Eligible participants will be entered on study centrally at DFCI by the Research Project Manager. All sites should call the Lead Site Research Project Manager, by phone with any questions.

Following registration, participants should begin protocol therapy as soon as feasible. Issues that would cause treatment delays should be discussed with the Overall PI. If a participant does not receive protocol therapy following registration, the participant's registration on the study must be canceled. The Research Project Manager should be notified of cancellations as soon as possible.

4.4 Registration Process for Other Investigative Sites

To register a participant, the following documents should be completed by the research nurse or data manager and e-mailed to the Lead Site Research Project Manager:

- Copy of labs and clinical information that satisfy inclusion criteria
- Signed participant consent form
- HIPAA authorization form
- Registration Form

The research nurse or data manager at the participating site will then e-mail the Lead Site Research Project Manager, to verify eligibility. To complete the registration process, the Coordinator will follow DF/HCC Standard Operating Procedure for Human Subject Research Titled *Subject Protocol Registration* (SOP #: REGIST-101) and register the participant on the protocol. The coordinator will e-mail the participant study number, and if applicable the dose treatment level, to the participating site. The coordinator will also call the research nurse or data manager at the participating site and verbally confirm registration.

CONFIDENTIAL

This document is confidential. Do not disclose or use except as authorized.

Treatment may not begin without confirmation from the Coordinating Center that the participant has been registered.

NOTE: Registration can only be conducted during the business hours of 8:00 AM and 5:00 PM Eastern Time Monday through Friday.

Same day treatment registrations will only be accepted with prior notice and discussion with the Coordinating Center.

5. TREATMENT PLAN

5.1 Treatment Regimen

Daratumumab is to be administered as described in the table below per local standard of care. Reasons for early discontinuation of treatment are listed in Section 8.3.

Agent	Pre-medications/ Precautions	Dose	Route	Schedule	Cycle Length
Daratumumab	Please see section 5.2.1.3 for a list of pre-medications and post-medications	16 mg/kg	Intravenous	Q1 Week Cycles 1-2	4 Weeks
				Q2 Weeks Cycles 3-6	
				Q4 Weeks Cycles 7-20	

There is no maintenance therapy. Assessment of myeloma and progression will be performed at the beginning of each cycle, EOT, and every 3 months thereafter.

5.2 Agent Administration

5.2.1 Daratumumab

5.2.1.1 Daratumumab Preparation

The infusion solution will be prepared on the day of the planned infusion. Please see section 11.1 for detailed instructions for preparation of daratumumab.

5.2.1.2 Daratumumab Administration

Daratumumab (16 mg/kg) will be administered by IV infusion to subjects:

CONFIDENTIAL

This document is confidential. Do not disclose or use except as authorized.

- Weekly during cycles 1 and 2
- Every other week during cycles 3 through 6
- Monthly during cycles 7 through 20

Each subject's dose will be calculated per local institutional standards. There is no cap on the absolute dose allowed, as long as the dose does not exceed 16 mg/kg. Subjects will receive pre-infusion medications and post-infusion medications as outlined in Section 5.2.1.3. Every effort should be made to keep subjects on the planned dosing schedule.

Please see Section 11.1 and site SOPs for administration of commercial daratumumab for full detailed instructions for administration of daratumumab.

5.2.1.3 Guidelines for Prevention of Infusion Reactions

Pre-Infusion Medication

Pre-infusion medications for subjects receiving daratumumab should be administered as described in Table 5 at the minimum, however sites may follow local guidelines for pre-infusion medications if more robust. On daratumumab infusion days, subjects should receive the following medications prior to infusion:

- Paracetamol (acetaminophen) 650-1000 mg IV or orally (PO) approximately 1 hour prior to daratumumab infusion.
- An antihistamine (diphenhydramine 25-50 mg IV or PO, or equivalent) approximately 1 hour prior to daratumumab infusion.
- Approximately 1 hour prior to daratumumab infusion, methylprednisolone IV 100 mg for the first 2 infusions, 60 mg for all subsequent infusions (in the absence of infusion related AEs in the first 2 infusions). An equivalent intermediate-acting or a long-acting corticosteroid may substitute. IV administration is required prior to the first 2 infusions, but oral steroids may be substituted with subsequent infusions.

Post-Infusion Medication

For the prevention of delayed infusion-related reactions, all subjects are recommended to receive corticosteroid orally (20 mg methylprednisolone or equivalent in accordance with local standards) 24 hours and 48 hours following daratumumab infusions for the first cycle of therapy, after which it is at the treating physician's discretion. Sites should follow the above and below outlined post-infusion medications at the minimum, however sites may follow local guidelines for post-infusion medications if more robust.

For subjects with higher risk of respiratory complications (ie, subjects who have a FEV1 <80% or subjects with asthma), the following post-infusion medications are recommended:

- Antihistamine (diphenhydramine or equivalent) 24 hours and 48 hours following all daratumumab infusions

CONFIDENTIAL

This document is confidential. Do not disclose or use except as authorized.

- Short-acting β_2 adrenergic receptor agonist such as salbutamol aerosol
- Control medications for lung disease (eg, inhaled corticosteroids \pm long-acting β_2 adrenergic receptor agonists for subjects with asthma; long-acting bronchodilators such as tiotropium or salbutamol \pm inhaled corticosteroids for subjects with COPD)

In addition, these at-risk subjects may be hospitalized for monitoring for up to 2 nights after an infusion. If subjects are hospitalized, then their FEV1 should be measured before discharge. If these subjects are not hospitalized, then a follow up telephone call should be made to monitor their condition within 48 hours after all infusions. If the subject has not experienced a significant medical event but is hospitalized overnight (under 24 hours) only for observation, then the hospitalization should not be reported as a serious adverse event (SAE). Investigators may prescribe bronchodilators, antihistamines, and corticosteroids that are deemed necessary to provide adequate supportive care in the event a bronchospasm occurs after subjects are released from the hospital/clinic. If, after 4 full doses, an at-risk subject experiences no major infusion-related reactions, then post-infusion medications may be stopped at the investigator's discretion.

Table 5: Time and Events Schedule for Pre- and Post-Infusion Medication

Cycle (each cycle is 4 weeks in length)		Cycle 1				Cycle 2				Cycle 3 - 6		Cycle 7 - 20
Day During Cycle		D1	D8	D15	D22	D1	D8	D15	D22	D1	D15	D1
Study Drug Administration Refer to Section 11.1 for recommendations on daratumumab infusion rate.												
Daratumumab Administration		X	X	X	X	X	X	X	X	X	X	X
Pre-Infusion Medications												
Methylprednisolone (IV)	Methylprednisolone 100 mg for first 2 infusions, 60 mg for all subsequent infusions. Substitutions allowed.	approximately 1 hr prior to every infusion of daratumumab										
Antihistamine (IV or PO)	Diphenhydramine 25-50 mg or equivalent	approximately 1 hr prior to every infusion of daratumumab										
Paracetamol (IV or PO)	Paracetamol or acetaminophen 650-1000 mg	approximately 1 hr prior to every infusion of daratumumab										
Post-Infusion Medications												
Methylprednisolone (PO)	Methylprednisolone 20 mg/day orally or equivalent	24 hours and 48 hours days following daratumumab infusions in cycle 1 (beginning the day after the infusion). Treatment with methylprednisolone 24 hours and 48 hours following infusion after the first cycle is at the discretion of the treating physician.										
Antihistamine (PO)	Antihistamine (diphenhydramine or equivalent) 24 and 48 hours following all daratumumab infusions	For subjects with higher risk of respiratory complications (ie, subjects who have a FEV1 <80% or subjects with asthma), the following post-infusion medications are recommended. If, after 4 full doses, an at-risk subject experiences no major infusion-related reactions, then post-infusion medications may be stopped at the investigator's discretion.										
β2 adrenergic receptor (INH)	Short-acting β2 adrenergic receptor agonist such as salbutamol aerosol											
Control Medications for lung disease (INH)	Control medications for lung disease (eg, inhaled corticosteroids ± long-acting β2 adrenergic receptor agonists for subjects with asthma; long-acting bronchodilators such as tiotropium or salbutamol ± inhaled corticosteroids for subjects with COPD)											

CONFIDENTIAL

This document is confidential. Do not disclose or use except as authorized.

5.2.1.4 Management of Infusion-Related Reactions

Subjects should be carefully observed during daratumumab infusions. Trained study staff at the clinic should be prepared to intervene in case of any infusion reactions occurring, and resources necessary for resuscitation (eg, agents such as epinephrine and aerosolized bronchodilator, also medical equipment such as oxygen tanks and a defibrillator) should be available at the bedside. Attention to staffing should be considered when multiple subjects will be dosed at the same time.

If an infusion-related reaction develops, then the infusion should be temporarily interrupted or slowed down. Subjects who experience AEs during the infusion should be treated according to the investigator's judgment and best clinical practice. The following guidelines may apply:

- Subjects should be treated with acetaminophen, antihistamine, or corticosteroids. Intravenous saline may be indicated. For bronchospasm, urticaria, or dyspnea, subjects may require antihistamines, oxygen, corticosteroids, or bronchodilators. For hypotension, subjects may require vasopressors.
- In the event of a life-threatening infusion-related reaction (which may include pulmonary or cardiac events), or anaphylactic reaction, daratumumab should be discontinued and no additional daratumumab should be administered to the subject. Aggressive symptomatic treatment should be applied.

If an infusion is paused or the infusion rate is decreased, then a longer-than-anticipated infusion time may occur. Overnight stays at the hospital because of slow infusion times should not be reported as an SAE. However, if the underlying cause of the delayed infusion time is an AE or SAE, then that should be reported as such.

Infusion-Related Events of Grade 1 or Grade 2

If the site investigator assesses an AE to be related to the daratumumab infusion, then the infusion should be paused. When the subject's condition is stable, the infusion may be restarted at the site investigator's discretion. Upon restart, the infusion rate should be half of that used before the interruption. Subsequently, the infusion rate may be increased at the site investigator's discretion.

If the subject experiences a Grade 2 or higher event of laryngeal edema or a Grade 2 or higher event of bronchospasm that does not respond to systemic therapy and does not resolve within 6 hours from the onset, then the subject should be withdrawn from treatment after discussion with the overall principal investigator.

Infusion-Related Reactions of Grade 3 or Higher

For infusion-related AEs that are Grade 3 or higher, the daratumumab infusion should be stopped, and the subject should be observed carefully until the resolution of the AE or until the intensity of the event decreases to Grade 1. The subject must be withdrawn from treatment after discussion with the overall principal investigator.

CONFIDENTIAL

This document is confidential. Do not disclose or use except as authorized.

5.2.1.5 Hepatitis B Virus Serology Testing, and Management

HBV Serology

All subjects will be tested locally for hepatitis B surface antigen (HBsAg), hepatitis B surface antibody (Anti-HBs), and hepatitis B core antibody (Anti-HBc) at Screening. Additionally, subjects who are currently in the treatment phase of the study who are within 6 months of starting study treatment when Protocol Amendment 11 is implemented will be required to have HBV serology performed locally upon signing the updated ICF.

HBV serology is not required at Screening or for subjects ongoing in the Treatment Phase who are within 6 months of starting study treatment if this was performed as part of standard of care within 3 months prior to first dose.

HBV DNA Tests:

Subjects who are positive for Anti-HBc or Anti-HBs will undergo testing for hepatitis B DNA by PCR. Subjects with serologic findings suggestive of HBV vaccination (Anti-HBs positivity as the only serologic marker) and a known history of prior HBV vaccination do not need to be tested for HBV DNA by PCR. During and following study treatment, subjects who have history of HBV infection will be closely monitored for clinical and laboratory signs of reactivation of HBV as specified in the Study Calendar (Section 10). Where required by local law, the results of HBV testing may be reported to the local health authorities.

Management of Hepatitis B Virus Reactivation

Primary antiviral prophylaxis is permitted as per local standard of care. Per protocol, HBV DNA testing by PCR is mandatory for subjects at risk for HBV reactivation see Section 10.

For subjects who are diagnosed with HBV reactivation while on treatment, study treatment should be interrupted until the infection is adequately controlled. If the benefits outweigh the risks, study treatment may be resumed with concomitant antiviral prophylaxis as per local standard of care. Consult a liver disease specialist as clinically indicated.

Table 6: Testing and Monitoring

	Screening Phase	Treatment Phase		Follow-up Phase		Notes
	Within 42 days of registration	Day 1 of each cycle (28-day cycles)	EOT within 30 days of last dose	Up to 6 months	After 6 months: Testing per standard of care	
Laboratory Assessments						
Hepatitis B (HBV) serology	X					Local testing for hepatitis B surface antigen (HBsAg), hepatitis B surface antibody (Anti-HBs), and hepatitis B core antibody (Anti-HBc). Refer to Section 5.2.1.5

CONFIDENTIAL

This document is confidential. Do not disclose or use except as authorized.

HBV DNA testing	X	Q12W during treatment, at the End of Treatment Visit, and Q12W for up to 6 months after the last dose of study treatment	For subjects with serologic evidence of resolved HBV infection (i.e., positive Anti-HBs or positive Anti-HBc) at Screening, HBV DNA testing by PCR must be performed locally. Refer to Section 5.2.1.5
-----------------	---	--	---

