6.1 Daratumumab Toxicity Management

Refer to Section 5.2.1.4 for details on management of infusion-related reactions. If any of the following criteria are met, then the daratumumab infusion should be held (**delayed not omitted**) to allow for recovery from toxicity.

Hematologic Toxicities: For adverse hematologic events that are considered possibly, probably or definitely related to Daratumumab, the following criteria for retreatment and dose modification should be followed. Treatment may be delayed for a maximum of 14 days. Holds other than described below may occur at the investigator’s discretion, after discussion with the overall principal investigator.

Table 7 Daratumumab Hematologic Toxicities

CTCAE 4.0 Category	CTCAE Grade	Daratumumab Dose Modification
Thrombocytopenia (with bleeding)	≤ Grade 2	Hold dose until resolved to ≤ Grade 1
	≥ Grade 3	Discontinue study medication
Febrile Neutropenia	≤ Grade 2	Hold dose until resolved to < Grade 1
	≥ Grade 3	Discontinue study medication
Neutropenia with Infection	≤ Grade 2	Hold dose until resolved to < Grade 1
	≥ Grade 3	Discontinue study medication
All other related toxicities not listed	≤ Grade 2	Hold dose until resolved to ≤ Grade 1

CONFIDENTIAL

This document is confidential. Do not disclose or use except as authorized.

previously in this table	≥ Grade 3	Discontinue study medication
---------------------------------	------------------	------------------------------

Non Hematologic Toxicity: For adverse non hematologic events that are considered to be possibly, probably or definitely related to daratumumab, the following criteria for retreatment and dose modification should be followed. The treating investigator should determine the clinical significance of laboratory values or radiographic findings and attribution to study medications before a treatment decision is made. Treatment may be delayed for a maximum of 14 days. Holds other than described below may occur at the investigator’s discretion, after discussion with the overall principal investigator.

Table 8 Daratumumab Non-Hematologic Toxicities

CTCAE 4.0 Category	CTCAE Grade	Daratumumab Dose Modification
All non-hematologic toxicities:	≤ Grade 2	Hold dose until resolved to ≤ Grade 1
	≥ Grade 3	Discontinue study medication

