6.2 Daratumumab Delays

Administration of daratumumab may be restarted upon recovery from toxicity to Grade 1 or below, with the exception that Grade 2 laryngeal edema or Grade 2 bronchospasm must be fully recovered. If more than 2 consecutive planned doses of daratumumab are delayed due to AEs, treatment should be permanently discontinued after discussion with the overall principal investigator.

If 2 consecutive doses of daratumumab are delayed for any reason other than AEs, this should be brought to the attention of the Principal Investigator at the earliest possible time and study treatment should be discontinued, unless, upon consultation with the overall Principal Investigator and the review of safety and efficacy, continuation is agreed upon. Documentation of this discussion should be placed in the research chart or medical record. Delays for vacations or non-AE related events may be held for a maximum of 7 days. If held for longer, a discussion with the overall PI must occur to discuss whether the participant may remain on study.

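### For a daratumumab-related HBV reactivation of Grade 3 or higher, Section 5.2.1.5 permits treatment to resume while Table 8 requires discontinuation, and the protocol does not say which governs

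*Combined protocol and SAP*

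**What the plan says.** Four provisions of the protocol bear on a patient whose hepatitis B reactivates on treatment.

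- **Section 5.2.1.5 (HBV management).** On reactivation, "study treatment should be interrupted until the infection is adequately controlled". The next sentence reads: "If the benefits outweigh the risks, study treatment may be resumed with concomitant antiviral prophylaxis as per local standard of care". Neither sentence mentions CTCAE grade, a maximum length of hold, or contact with the overall PI.
- **Section 6.1, Table 8.** The lead-in sets the scope: "For adverse non hematologic events that are considered to be possibly, probably or definitely related to daratumumab". The single category is "All non-hematologic toxicities". At Grade 2 or lower the instruction is "Hold dose until resolved to ≤ Grade 1"; at Grade 3 or higher it is "Discontinue study medication".
- **Section 6.1, length of delay.** "Treatment may be delayed for a maximum of 14 days". The sentence after it allows the investigator to use holds other than those described, once the overall PI has been consulted.
- **Section 6.2.** "If more than 2 consecutive planned doses of daratumumab are delayed due to AEs, treatment should be permanently discontinued", after discussion with the overall PI. The same paragraph allows restart on recovery to Grade 1 or below.

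Section 6.1 refers the reader to 5.2.1.4 for infusion reactions. It does not refer to 5.2.1.5, and 5.2.1.5 does not refer to Section 6.

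**The concern.** The protocol expects this event. Section 3.2.11 admits patients with resolved HBV who are PCR-negative, Sections 5.2.1.5 and 10 have them tested for HBV DNA every 12 weeks on treatment, and Section 9.8 lists HBV reactivation as an adverse event of special interest. It is therefore an adverse event in the protocol's own terms and, if attributed to the drug, falls within Table 8.

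For a related case of Grade 3 or higher, a site working from Table 8 stops treatment for good, while a site working from 5.2.1.5 may re-treat. Both can cite the protocol. What is at stake is consistent safety handling across centers, the patient's exposure, whether re-treatment counts as a protocol departure (Appendix D, 3.8.2), and the reason for removal that Section 8.3 requires to be recorded.

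**Working it through.** The plan states no figure on this point, so there is none to reproduce. The check sets the rules side by side and then does calendar arithmetic on the two delay limits.

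**Rules by type of case**

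| Reactivation | 5.2.1.5 | Section 6 | Relation |
|---|---|---|---|
| Related, Grade 3 or higher | Hold; may resume once controlled | Table 8: discontinue | One permits what the other forbids |
| Related, Grade 2 or lower, short hold | Hold; may resume once controlled | Table 8: hold, then retreat | Compatible |
| Related, Grade 2 or lower, hold beyond 14 days | No time limit | 6.1: 14-day maximum, other holds possible after PI discussion | Tension |
| More than 2 consecutive doses delayed for AEs | No dose limit | 6.2: permanent discontinuation after PI discussion | Tension |
| Judged unrelated | Hold; may resume once controlled | Outside Table 8 | No Table 8 conflict |

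**When each delay limit is reached**

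Inputs: dosing intervals of 7 days (cycles 1-2), 14 days (cycles 3-6) and 28 days (cycles 7-20), from Section 1.3; the 14-day maximum from 6.1; the more-than-2-doses trigger from 6.2. Days count from the first delayed dose. Planned doses are assumed to stay on the original calendar.

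The third consecutive planned dose falls at 2 × interval:

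- weekly: 2 × 7 = day 14
- 2-weekly: 2 × 14 = day 28
- 4-weekly: 2 × 28 = day 56

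The 14-day maximum is thus reached at the same time as the 6.2 trigger under weekly dosing, and before it in the other phases. If control were judged only at the next scheduled HBV DNA test, the hold could last up to 12 × 7 = 84 days and pass both limits in every phase. That is an assumption, since unscheduled tests are possible.

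**How many patients**

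The documents give no HBV rates. Assume 5-15% of the 50 patients have resolved infection and 1-10% of those reactivate:

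- low: 50 × 0.05 × 0.01 = 0.025 patients
- high: 50 × 0.15 × 0.10 = 0.75 patients

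This counts reactivations of any grade and attribution. The group in direct conflict (related, Grade 3 or higher) can only be the same size or smaller.

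**The case against.** The strongest reply is that 5.2.1.5 is an event-specific rule under its own heading and Section 6 is the general toxicity rule, so the specific one should prevail. That reading is open, but no passage adopts it. Section 6.1 points to a special rule for infusion reactions and is silent on the one for HBV.

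A second reply is that the discretion clause in 6.1 covers an HBV hold. This has force for the 14-day maximum: the hold can be read as one of the other holds allowed after PI discussion, and the 14-day sentence does not itself order discontinuation. The clause concerns holds, however, and does not undo the Grade 3 row of Table 8.

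A reader might go further and infer that Section 6 ends treatment for any HBV reactivation, so that sites receive opposite instructions throughout. The documents do not support that. Table 8 discontinues only at Grade 3 or higher and only with attribution; below that it holds and retreats. Section 6.2 needs more than 2 consecutive delayed doses, which in cycles 7-20 (14 of the 20 cycles) takes until day 56, and it allows restart on recovery. Section 5.2.1.5 permits resumption without requiring it, so a site that stops permanently at Grade 3 breaches neither section.

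**Conclusion.** The inconsistency is real and confined to a subset. For a related HBV reactivation of Grade 3 or higher, 5.2.1.5 leaves open a return to treatment that Table 8 closes, and nothing in the protocol resolves it. For longer holds at lower grades the sections are in tension, with a discretion clause in 6.1 that partly relieves it.

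The expected number affected is below one patient even at the upper end of the assumed rates (0.75 reactivations of any grade). How many would be Grade 3 or higher cannot be stated from the documents. An effect on the primary endpoint is not shown and would be small. The reason to correct the text is that two written rules disagree on a named adverse event of special interest in a multi-center trial. Which rule is clinically right is not judged here.

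**What to change.** Reconcile Sections 5.2.1.5, 6.1 (with Table 8) and 6.2. State which section governs HBV reactivation, and say separately whether the Grade 3 discontinuation, the 14-day maximum and the 2-dose limit apply to it. If 5.2.1.5 governs, write the exemption into 6.1 and 6.2. If Section 6 governs, limit the resumption sentence in 5.2.1.5 to match. Cross-refer both ways. The clinical team makes the choice.

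The cost is one or two sentences in the next amendment. It adds no procedures or data collection and does not change the statistical design.
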